18.7 Measurement-Based Response Assessment According to the Lugano Classification

Complete Response	Complete radiologic response (all of the following)		Complete metabolic response (even with a persistent mass)
	Lymph nodes and extralymphatic sites	
 
Target nodes/nodal masses must regress to <math>\leq 1.5</math> cm in longest diameter.
 
No extralymphatic sites of disease.
 
	
 
Score <math>\leq 3^*</math> with or without a residual mass on 5-point scale†.
 
It is recognized that in Waldeyer's ring or extranodal sites with high physiologic uptake or with activation within spleen or marrow (e.g., with chemotherapy or myeloid colony-stimulating factors), uptake may be greater than normal mediastinum and/or liver. In this circumstance, complete metabolic response may be inferred if uptake at sites of initial involvement is no greater than surrounding normal tissue even if the tissue has high physiologic uptake.
 

Nonmeasured lesion	Absent		Not applicable
Organ enlargement	Regress to normal		Not applicable
New lesions	None		None
Bone marrow	Normal by morphology; if determinate, IHC negative		No evidence of FDG-avid disease in marrow
Partial Response	Partial remission (all of the following)		Partial metabolic response
	Lymph nodes and extralymphatic sites	
 
<math>\geq 50\%</math> decrease in SPD of up to 6 target measurable nodes and extranodal sites
 
When a lesion is too small to measure on CT, assign 5 mm X 5 mm as the default value
 
When no longer visible, 0 X 0 mm
 
For a node <math>> 5</math> mm X 5 mm, but smaller than normal, use actual measurement for calculation
 
	
 
Score 4 or 5† with reduced uptake compared with baseline and residual mass(es) of any size
 
At interim, these findings suggest responding disease
 
At end of treatment, these findings indicate residual disease
 

Nonmeasured lesion	Absent/normal, regressed, but no increase		Not applicable
Organ enlargement	Spleen must have regressed by $> 50\%$ in length beyond normal		Not applicable
New lesions	None		None
Bone marrow	Not applicable		Residual uptake higher than uptake in normal marrow but reduced compared with baseline (diffuse uptake compatible with reactive changes from chemotherapy allowed). If there are persistent focal changes in the marrow in the context of a nodal response, consideration should be given to further evaluation with MRI or biopsy or an interval scan

No response or stable disease	Stable disease		No metabolic response
	Target nodes/nodal masses, extranodal lesions	< 50% decrease from baseline in SPD of up to 6 dominant, measurable nodes and extranodal sites; no criteria for progressive disease are met	Score 4 or 5† with no significant change in FDG uptake from baseline at interim or end of treatment
	Nonmeasured lesion	No increase consistent with progression	Not applicable
	Organ enlargement	No increase consistent with progression	Not applicable
	New lesions	None	None
	Bone marrow	Not applicable	No change from baseline
Progressive disease	Progressive disease requires at least 1 of the following		Progressive metabolic disease
	Individual target nodes/nodal masses	PPD progression:	Score 4 or 5 with an increase in intensity of uptake from baseline and/or
	Extranodal lesions	An individual node/lesion must be abnormal with: 
 
Longest diameter (LDi) > 1.5 cm and
 
Increase by <math>\geq 50\%</math> from PPD nadir and
 
An increase in LDi or smallest diameter (SDi) from nadir
 
0.5 cm for lesions <math>\leq 2</math> cm
 
1.0 cm for lesions <math>> 2</math> cm
 
In the setting of splenomegaly, the splenic length must increase by <math>> 50\%</math> of the extent of its prior increase beyond baseline (e.g., a 15-cm spleen must increase to 16 cm). If no prior splenomegaly, must increase by at least 2 cm from baseline
 
New or recurrent splenomegaly
 
	
 
New FDG-avid foci consistent with lymphoma at interim OR end-of-treatment assessment
 

	Nonmeasured lesion	New or clear progression of preexisting nonmeasured lesions	None
	New lesions	
 
Regrowth of previously resolved lesions
 
A new node <math>> 1.5</math> cm in any axis
 
A new extranodal site <math>< 1.0</math> cm in any axis; if <math>> 1.0</math> cm in any axis, its presence must be unequivocal and must be attributable to lymphoma
 
Assessable disease of any size unequivocally attributable to lymphoma
 
	
 
New FDG-avid foci consistent with lymphoma rather than another etiology (e.g., infection, inflammation).
 
If uncertain regarding etiology of new lesions, biopsy or interval scan may be considered.
 

	Bone marrow	New or recurrent involvement	New or recurrent FDG-avid foci

18.8 Instructions for the SWOG Biospecimen Bank – Lab #201, Solid Tissue, Myeloma and Lymphoma Division

a. **Formalin-Fixed Paraffin-Embedded (FFPE) Tissue:** The SWOG Biospecimen Bank will receive FFPE specimens as either blocks or slides/sections at baseline.

1. If tissue block is received, then upon receipt, Bank will cut 1 H&E slide for Pathology Review. Any remaining tissue (in block) will be stored at room temperature. (Priority of slides for planned future TM objectives will be specified in a forthcoming revision.)
2. If slides are received, then 1 H&E slide will be scanned for Pathology Review and then all unstained slides will be stored refrigerated (2-8°C) and under desiccant, until distribution for planned future TM objectives.

a. Pathology review:

For each case, the Bank will scan 1 H&E slide to digital images at 40x magnification. The digital images and corresponding redacted pathology reports will be sent to study pathologists for QC pathology review. Case review will be split amongst the following pathologists and will be sent in batches throughout the duration of accrual.

b. The following pathologists will conduct Pathology review:

[name].  
City of Hope Medical Center  
[name]  
[name]  
[contact] [name]  
[contact]  
Email: [[contact]](mailto:[contact])

[name].  
Department of Laboratory Medicine and Pathology  
Mayo Clinic  
[name]  
[name]  
[contact]  
[contact]  
Email: [[contact]](mailto:[contact])

[name].  
Department of Pathology  
University of Michigan  
[name]  
[name]  
[contact]  
[contact]  
Email: [[contact]](mailto:[contact])

[name].  
Department of Pathology and Laboratory Medicine  
Children's Hospital Los Angeles  
[name]  
[name]

[contact]  
[contact]  
Email: [[contact]](mailto:[contact])

b. **Peripheral Blood in cfDNA Streck Tubes:** The SWOG Biospecimen Bank will receive ambient peripheral blood in cfDNA Streck tubes at up to 4 timepoints. Upon receipt, the Bank will accession and process for plasma and buffy coat. Plasma is processed using the following double-centrifugation protocol: 1,500xg for 10 minutes at room temperature with brake (buffy coat is removed at this point); plasma is removed and centrifuged again at 3,000xg for 10 minutes at room temperature with brake. Plasma will be stored in 1-mL aliquots, and buffy coat will be stored as 1 aliquot; both plasma and buffy coat will be banked in a -80°C freezer until distribution. Planned future correlatives (ctDNA analysis) are planned for incorporation with a forthcoming revision.

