\* For patients who are contra-indicated for PET-CT, see [Section 18.7](#) for Measurement-based Response Assessment According to the Lugano Classification.

10.2 **Best Response:**

- a. CR: One objective status of CR documented before relapse.
- b. PR: One objective status of PR documented before progression but not qualifying as a CR.
- c. Stable: At least one objective status of stable documented at least 6 weeks after registration, not qualifying as anything else above.
- d. Increasing Disease: Objective status of progression.
- e. Inadequate assessment, response unknown: No other response category applies.

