#### 10.4 **Progression Free Survival (PFS)**

From date of registration to date of first observation of progressive disease according to the 2014 Lugano classification, or death due to any cause. Patients last known to be alive and without report of progression are censored at date of last contact. See [Sections 10.1b.4](#) and [18.7](#) for definition of progressive disease according to 2014 Lugano classification.

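### Wrong as written, subject to a source-page check (minor): the CT rule in 18.7 puts the attribution test on the larger new extranodal lesion and none on the smaller, and 10.4 cites 18.7 for PFS progression

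*Combined protocol and SAP*

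**What the plan says.** Section 18.7 is a two-column table, with CT criteria on the left and metabolic criteria on the right. In the CT column the progressive-disease block opens with "Progressive disease requires at least 1 of the following", so any single item is enough. The new-lesion cell includes these bullets:

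- For a node: "A new node > 1.5 cm in any axis".
- For an extranodal site: "A new extranodal site < 1.0 cm in any axis; if > 1.0 cm in any axis, its presence must be unequivocal", followed by the condition that it be attributable to lymphoma.
- For everything else: "Assessable disease of any size unequivocally attributable to lymphoma".

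A separate row of the same block admits a nonmeasured lesion that is new, or an existing one that has clearly progressed. It gives no size limit.

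The table reaches the primary endpoint through Section 10.4, which points to 10.1b.4 and 18.7 "for definition of progressive disease according to 2014 Lugano classification". EFS (10.5) also counts progression. The express scope of 18.7 is the note closing the response criteria in 10.1: "For patients who are contra-indicated for PET-CT, see" Section 18.7. All patients have a contrast-enhanced CT at 1 and 2 years (7.6a), and 14.4f treats these scans as disease assessments with a tumor assessment form.

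**The concern.** A small, uncertain extranodal finding is normally harder to call than a large one, so one expects the stricter test on the smaller lesion. The bullet as supplied does the reverse. Taken literally, an equivocal 0.4 cm spot is progression and an equivocal 3.0 cm mass is not.

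What is at stake is the classification of PFS events, and through progression EFS events, in two directions: a false event from a small equivocal site, and a missed or late event from a larger equivocal site. Response is assessed on local radiology review (7.4), so sites work from the printed wording.

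**Working it through.** No figure in the plan depends on this bullet, so there is nothing to reproduce. The check sets the rules side by side.

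**Step 1: direct comparators.** The two adjacent bullets bear on new lesions in the same cell.

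- The node bullet lets larger size qualify (above 1.5 cm) and asks for no attribution.
- The any-size bullet uses attribution to admit disease that size alone would not. If every new extranodal site below 1.0 cm already counts, that bullet has nothing to add for small extranodal sites.

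**Step 2: weaker support.** Growth of an existing node or lesion requires "Longest diameter (LDi) > 1.5 cm and" further conditions, and the partial-response block says "When a lesion is too small to measure on CT, assign 5 mm X 5 mm as the default value". Both show that the table treats small CT findings with caution, but neither is a new-lesion rule.

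**Step 3: where the wording matters.** Compare the printed rule with the same rule with its two signs exchanged. The exchange is only a device for finding the sensitive cases; it is not a proposed criterion. The any-size bullet is applied in both versions.

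| New extranodal site | Certainty | As printed | Signs exchanged |
|---|---|---|---|
| below 1.0 cm (0.4, 0.9) | unequivocal | progression | progression |
| below 1.0 cm (0.4, 0.9) | equivocal | progression | not progression |
| exactly 1.0 cm | unequivocal | progression | progression |
| exactly 1.0 cm | equivocal | not progression | not progression |
| above 1.0 cm (1.1, 3.0) | unequivocal | progression | progression |
| above 1.0 cm (1.1, 3.0) | equivocal | not progression | progression |

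Unequivocal, attributable lesions are progression in every row, so only equivocal lesions are sensitive. A site of exactly 1.0 cm is covered by neither sign.

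**Step 4: the nonmeasured-lesion row.** Any one criterion suffices. If that row is read to include a small new lesion, the equivocal site below 1.0 cm is progression under both versions and that difference disappears. The difference for an equivocal site above 1.0 cm remains, provided the site is one that is measured. So the count of sensitive cells, leaving aside exactly 1.0 cm, is two of four without that row and one of four with it. The plan does not say which reading applies.

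**Step 5: scale.** The final analysis is set at 179 PFS events (11.1), so one miscalled event would be 1/179 = 0.56% of them. This is true of any single event. The documents give neither the number of patients who cannot have PET-CT nor a rate of equivocal new extranodal lesions, so no expected number follows.

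**The case against.** The strongest objection is that the point rests on two inequality signs in a table read by a program, and the block shows layout damage: the 0.5 and 1.0 cm growth increments, for example, have come apart from the line they belong to. This stands as a reason to check the source page first. It does not dispose of the point, because both signs would have to be misread and the neighbouring signs read sensibly.

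Second, scope. The express scope is patients in whom PET-CT is contraindicated. Section 18.7 also has a metabolic column, so the citation in 10.4 does not by itself apply the CT column to everyone else. That is right. Reach to the 1- and 2-year CTs is only possible, and it arises because no section says whether 18.7 or 10.1b.4 governs them.

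Third, other safeguards make it less likely that an equivocal CT lesion alone settles progression. A PET-CT is required at progression (15.4a item 4) and before subsequent therapy (7.6c). Biopsy is strongly recommended before second-line therapy (7.4c). The 1- and 2-year images go for retrospective central review (14.4f). These limit the effect, but none is a condition of the event in 10.4, and the PET-CT cannot help patients for whom it is contraindicated.

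Fourth, a reader might infer that the signs should simply be exchanged. The documents do not establish that. The exchanged rule would count an equivocal site above 1.0 cm with no attribution test, in a trial that is itself concerned about false progressions on N-AVD (11.2, RT monitoring). The cited Lugano publication is not among the documents, and progression also ends protocol treatment (7.8b). The supportable statement is that the passages must be reconciled.

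**Conclusion.** The bullet is inconsistent with its two neighbours and, if both signs are confirmed on the source page, wrong as written. It is a minor defect in an endpoint rule. It can affect only equivocal new extranodal lesions read on CT criteria: one above 1.0 cm may be left uncalled, and one below 1.0 cm may be called progression, although the nonmeasured-lesion row might capture the latter anyway.

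The size of the effect is not derivable and is probably small, and its net direction is unknown. No alpha, power figure, event count or planned analysis changes.

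A reader might go further and infer that PFS is misdefined for the whole trial or that the comparison is biased toward one arm. The documents support neither. The express scope is narrow, PET-CT at progression limits the effect in patients who can have it, and nothing shows that such lesions would be read differently by arm.

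The conclusion assumes that the two signs are as supplied and that the any-size bullet is applied alongside the extranodal bullet.

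**What to change.** 1. Check both inequality signs on the source page. If they were misread, the sign question closes; the gaps at exactly 1.0 cm and over the follow-up CTs remain.
2. If they stand, reconcile the extranodal bullet with the two adjacent bullets, the nonmeasured-lesion row and the 2014 Lugano publication cited in 18.1. Say which branch covers exactly 1.0 cm.
3. Add one sentence stating whether 18.7 or 10.1b.4 governs PFS at the 1- and 2-year CTs.
4. Query any progression call, or decision not to call, that rests solely on a new extranodal lesion on CT.

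The cost is a one-line correction, one added sentence and a targeted data query. For the 1- and 2-year CTs, the query can use images that 15.4a items 5 and 6 already require sites to submit. The sample size and analysis plan need no change.

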18.9 CYP1A2 and CYP3A Inhibitors and Inducers

	Strong inhibitors	Moderate inhibitors	Weak inhibitors
CYP1A2	ciprofloxacin, enoxacin, fluvoxamine (a) , zafirlukast	methoxsalen, mexiletine, oral contraceptives	acyclovir, allopurinol, cimetidine, peginterferon alpha-2a, piperine, zileuton
CYP3A	boceprevir, cobicistat (c) , conivaptan (c) , danoprevir and ritonavir (d) , elvitegravir and ritonavir (d) , grapefruit juice (e) , indinavir and ritonavir (d) , itraconazole (c) , ketoconazole, lopinavir and ritonavir (c,j) , paritaprevir and ritonavir and (ombitasvir and/or dasabuvir) (d) , posaconazole, ritonavir (c,d) , saquinavir and ritonavir (c,d) , telaprevir (c) , tipranavir and ritonavir (c,d) , troleandomycin, voriconazole	aprepitant, cimetidine, ciprofloxacin, clotrimazole, crizotinib, cyclosporine, dronedarone (c) , erythromycin, fluconazole (b) , fluvoxamine (a) , imatinib, tofisopam, verapamil (c)	chlorzoxazone, cilostazol, fosaprepitant, istradefylline, ivacaftor (c) , lomitapide, ranitidine, ranolazine (c) , tacrolimus, ticagrelor (c)
	clarithromycin (c) , diltiazem (c) , idelalisib, nefazodone, nelfinavir (c)		

1. Note: Strong, moderate, and weak inhibitors are drugs that increase the AUC of sensitive index substrates of a given metabolic pathway  $\geq 5$ -fold,  $\geq 2$  to  $<5$ -fold, and  $\geq 1.25$  to  $<2$ -fold, respectively. Strong inhibitors of CYP3A causing  $\geq 10$ -fold increase in AUC of sensitive index substrate(s) are shown above the dashed line.
2. This table is prepared to provide examples of clinical inhibitors and is not intended to be an exhaustive list. DDI data were collected based on a search of the University of Washington Metabolism and Transport Drug Interaction Database [Hachad et al. (2010), Hum Genomics, 5(1):61].
3. (a) Strong inhibitor of CYP1A2 and CYP2C19, and moderate inhibitor of CYP2D6 and CYP3A.  
(b) Strong inhibitor of CYP2C19 and moderate inhibitor of CYP2C9 and CYP3A.  
(c) Inhibitor of P-gp (defined as those increasing AUC of digoxin to  $\geq 1.25$ -fold).  
(d) Ritonavir is usually given in combination with other anti-HIV or anti-HCV drugs in clinical practice. Caution should be used when extrapolating the observed effect of ritonavir alone to the effect of combination regimens on CYP3A activities.  
(e) The effect of grapefruit juice varies widely among brands and is concentration-, dose-, and preparation-dependent. Studies have shown that it can be classified as a "strong CYP3A inhibitor" when a certain preparation was used (e.g., high dose, double strength) or as a "moderate CYP3A inhibitor" when another preparation was used (e.g., low dose, single strength).

4. Abbreviations: AUC: area under the concentration-time curve; CYP: cytochrome P450; DDI: drug-drug interaction; OATP1B1: organic anion transporting polypeptide 1B1; OAT3: organic anion transporter 3; P-gp: P-glycoprotein.

	Strong inducers	Moderate inducers	Weak inducers
CYP1A2		phenytoin (a) rifampin (b) , ritonavir (c) , smoking, teriflunomide	-
CYP3A	carbamazepine (d) , enzalutamide (e) , mitotane, phenytoin (b) , rifampin (a) , St. John's wort (f)	bosentan, efavirenz, etravirine, modafinil	armodafinil, rufinamide

1. Note: Strong, moderate, and weak inducers are drugs that decrease the AUC of sensitive index substrates of a given metabolic pathway by ≥80%, ≥50% to <80%, and ≥20% to <50%, respectively.
2. This table is prepared to provide examples of clinical index inducers and not intended to be an exhaustive list. DDI data were collected based on a search of the University of Washington Metabolism and Transport Drug Interaction Database [Hachad et al. (2010), *Hum Genomics*, 5(1):61].
  - (a) Strong inducer of CYP3A and moderate inducer of CYP1A2, CYP2C19.
  - (b) Strong inducer of CYP2C19, CYP3A, and moderate inducer of CYP1A2, CYP2B6, CYP2C8, CYP2C9.
  - (c) Strong inducer of CYP2C19 and moderate inducer of CYP1A2, CYP2B6, CYP2C9.
  - (d) Strong inducer of CYP2B6, CYP3A, and moderate inducer of CYP2C9.
  - (e) Strong inducer of CYP3A and moderate inducer of CYP2C9, CYP2C19, CYP3A.
  - (f) The effect of St. John's wort varies widely and is preparation-dependent.
3. Abbreviations: AUC: area under the concentration-time curve; CYP: cytochrome P450; DDI: drug-drug interaction.

18.10 PRO-CTCAE Common Terminology Criteria for Adverse Events (PRO-CTCAE) Instrument

a. General Information:

The PRO-CTCAE instruments will be used to assess Patient-Reported toxicity outcomes.

Clinician graded CTCAE is the adverse event safety standard. PRO-CTCAE is intended to enhance the quality of adverse event data reporting in clinical trials, provide data that complements and extends the information provided by clinician reporting using CTCAE, represent the patient perspective of the experience of symptomatic adverse events, and improve detection of potentially serious adverse events.

The selection of PRO-CTCAE should be complementary to the clinician identified AEs for ongoing monitoring.

Adverse Event Characteristics: PRO-CTCAE is not intended for expedited reporting, real time review, or safety reporting.

Routine Adverse Event Reporting: Symptomatic Adverse Events reported by patients through PRO-CTCAE are not safety reporting and may be presented with other routine AE data.

PRO-CTCAE (adult and pediatric) assessment tools are available in the following languages. Estimated time of completion: 10 minutes.

- PRO-CTCAE: Available in English, Spanish, and French
- Ped PRO-CTCAE: Available in English

PRO-CTCAE is not currently available on the Medidata Patient Cloud ePRO. Forms are accessible from the [S1826](#) protocol abstract page on the CTSU website at [www.ctsu.org](http://www.ctsu.org). Administration instructions are included in [Section 15.6](#).

Please refer to the [PRO-CTCAE Terms of Use](#) for more information.

b. Recall Period for the PRO-CTCAE measures is: 7 days

c. PRO-CTCAE Analyses

The examination of PRO-CTCAE is exploratory, given there are currently no standardized scoring rules for how to combine attributes into a single score or how best to analyze PRO-CTCAE data longitudinally. PRO-CTCAE responses are scored from 0 to 4. For each of the PRO-CTCAE adverse events examined, the scores for each attribute (frequency, severity and/or interference) will be presented descriptively using summary statistics at each assessment time. Additionally, the worst severity and/or interference over the entire course will be summarized.

d. Study-Specific PRO-CTCAE Questions for Adults ( $\geq 18$  years of age):

Solicited Adverse Events: The following adverse events are considered expected and their presence/ absence should be solicited and severity graded at timepoints indicated in [Section 9.0](#).

CTCAE Item - Adult	PRO-CTCAE Item (Attributes)
Mucositis oral	Mucositis oral (SI)
Nausea	Nausea (FS)
Vomiting	Vomiting (F)
Diarrhea	Diarrhea (F)
Abdominal pain	Abdominal pain (FSI)
Dyspnea	Shortness of breath (SI)
Cough	Cough (SI)
Rash	Rash (P)
Pruitis	Itchy Skin (S)
Peripheral Sensory Neuropathy	Numbness or tingling in hands or feet (SI)
Pain	Pain (FSI)
Myalgia	Aching muscles (FSI)
Arthralgia	Aching joints (FSI)
Decrease sexual interest	Decreased sexual interest (S)
Any other symptoms that you wish to report?	Other symptoms (PS)

**Attribute Acronyms:**

F: Frequency, S: Severity, I: Interference, P: Presence/Absence/Amount

Symptom AE	Attributes	PRO-CTCAE Items	Response options
Mucositis oral	Frequency	--	--
	Severity	In the last 7 days, what was the SEVERITY of your MOUTH OR THROAT SORES at their WORST?	None, Mild, Moderate, Severe, Very Severe
	Interference	In the last 7 days, how much did MOUTH OR THROAT SORES INTERFERE with your usual or daily activities?	Not at all, A little bit, Somewhat, Quite a bit, Very much
Nausea	Frequency	In the last 7 days, how OFTEN did you have NAUSEA?	Never, Rarely, Occasionally, Frequently, Almost constantly
	Severity	In the last 7 days, what was the SEVERITY of your NAUSEA at its WORST?	None, Mild, Moderate, Severe, Very Severe

Symptom AE	Attributes	PRO-CTCAE Items	Response options
	Interference	--	--
Diarrhea	Frequency	In the last 7 days, how OFTEN did you have LOOSE OR WATERY STOOLS (DIARRHEA/DIARRHOEA)?	Never, Rarely, Occasionally, Frequently, Almost constantly
	Severity	--	--
	Interference	--	--
Abdominal pain	Frequency	In the last 7 days, how OFTEN did you have PAIN IN THE ABDOMEN (BELLY AREA)?	Never, Rarely, Occasionally, Frequently, Almost constantly
	Severity	In the last 7 days, what was the SEVERITY of your PAIN IN THE ABDOMEN (BELLY AREA) at its WORST?	None, Mild, Moderate, Severe, Very Severe
	Interference	In the last 7 days, how much did PAIN IN THE ABDOMEN (BELLY AREA) INTERFERE with your usual or daily activities?	Not at all, A little bit, Somewhat, Quite a bit, Very much
Dyspnea	Frequency	--	--
	Severity	In the last 7 days, what was the SEVERITY of your SHORTNESS OF BREATH at its WORST?	None, Mild, Moderate, Severe, Very Severe
	Interference	In the last 7 days, how much did your SHORTNESS OF BREATH INTERFERE with your usual or daily activities?	Not at all, A little bit, Somewhat, Quite a bit, Very much
Cough	Frequency	In the last 7 days, what was the SEVERITY of	Never, Rarely, Occasionally,

Symptom AE	Attributes	PRO-CTCAE Items	Response options
		your COUGH at its WORST?	Frequently, Almost constantly
	Severity	In the last 7 days, how much did COUGH INTERFERE with your usual or daily activities?	None, Mild, Moderate, Severe, Very Severe
	Interference	--	--
Rash	Frequency	In the last 7 days, did you have any RASH?	Yes, No
	Severity	--	--
	Interference	--	--
Pruritis	Frequency	--	--
	Severity	In the last 7 days, what was the SEVERITY of your ITCHY SKIN at its WORST?	None, Mild, Moderate, Severe, Very Severe
	Interference	--	--
Peripheral Sensory Neuropathy	Frequency	--	--
	Severity	In the last 7 days, what was the SEVERITY of your NUMBNESS OR TINGLING IN YOUR HANDS OR FEET at its WORST?	None, Mild, Moderate, Severe, Very Severe
	Interference	In the last 7 days, how much did NUMBNESS OR TINGLING IN YOUR HANDS OR FEET INTERFERE with your usual or daily activities?	Not at all, A little bit, Somewhat, Quite a bit, Very much

Symptom AE	Attributes	PRO-CTCAE Items	Response options
Pain	Frequency	In the last 7 days, how OFTEN did you have PAIN?	Never, Rarely, Occasionally, Frequently, Almost constantly
	Severity	In the last 7 days, what was the SEVERITY of your PAIN at its WORST?	None, Mild, Moderate, Severe, Very Severe
	Interference	In the last 7 days, how much did PAIN INTERFERE with your usual or daily activities?	Not at all, A little bit, Somewhat, Quite a bit, Very much
Myalgia	Frequency	In the last 7 days, how OFTEN did you have ACHING MUSCLES?	Never, Rarely, Occasionally, Frequently, Almost constantly
	Severity	In the last 7 days, what was the SEVERITY of your ACHING MUSCLES at their WORST?	None, Mild, Moderate, Severe, Very Severe
	Interference	In the last 7 days, how much did ACHING MUSCLES INTERFERE with your usual or daily activities?	Not at all, A little bit, Somewhat, Quite a bit, Very much
Arthralgia	Frequency	In the last 7 days, how OFTEN did you have ACHING JOINTS (SUCH AS ELBOWS, KNEES, SHOULDERS)?	Never, Rarely, Occasionally, Frequently, Almost constantly
	Severity	In the last 7 days, what was the SEVERITY of your ACHING JOINTS (SUCH AS ELBOWS, KNEES, SHOULDERS) at their WORST?	None, Mild, Moderate, Severe, Very Severe

Symptom AE	Attributes	PRO-CTCAE Items	Response options
	Interference	In the last 7 days, how much did ACHING JOINTS (SUCH AS ELBOWS, KNEES, SHOULDERS) INTERFERE with your usual or daily activities?	Not at all, A little bit, Somewhat, Quite a bit, Very much
Decreased Sexual Interest	Frequency	--	--
	Severity	In the last 7 days, what was the SEVERITY of your DECREASED SEXUAL INTEREST at its WORST?	None, Mild, Moderate, Severe, Very Severe
	Interference	--	--
Do you have any other symptoms that you wish to report?		Do you have any other symptoms that you wish to report?	Yes, No
Please list any other symptoms: (5 slots to list)	Frequency	--	--
	Severity	In the last 7 days, what was the SEVERITY of this symptom at its WORST?	None, Mild, Moderate, Severe, Very Severe
	Interference	--	--

e. Pediatric PRO-CTCAE Questions:

CTCAE Item - Pediatric	PRO-CTCAE Item (Attributes)
Mucositis oral	Mucositis oral (FSI)
Nausea	Nausea (FSI)
Vomiting	Vomiting (FI)
Diarrhea	Diarrhea (FI)
Abdominal pain	Abdominal pain (FSI)
Dyspnea	Shortness of breath (FSI)

Cough	Cough (FSI)
Rash acneiform	Pimples (bumps on face or chest) (S)
Pruitis	Itchy Skin (SI)
Peripheral Sensory Neuropathy	Numbness or tingling in hands or feet (SI)
Pain	Pain (FSI)
Myalgia	Aching muscles (FSI)
Arthralgia	Aching joints (FSI)

